Separate evaluations for third line use of axitinib following prior therapy with sunitinib in the first line followed by e.g. nivolumab, cabozantinib, or lenvatinib/everolimus in the second line are urgently needed. The efficacy of axitinib can continue to be documented after directly preceding therapy with sunitinib. These investigations allow a comparison of the efficacy and tolerability of axitinib in different lines.

Therefore, the following information is of particular interest during the course of the investigation:

- Efficacy (maximum response, survival time, progression-free time)
- Treatment tolerability (assessment by physician)
- Safety profile (overall incidence of adverse events and rate of side effects) of patients with advanced RCC, r/rMCL and GIST receiving treatment with temsirolimus, sunitinib, or axitinib
- Profile, comorbidities and characteristics of patients receiving treatment with temsirolimus, sunitinib, or axitinib
- The sequence of systemic therapies for advanced RCC, MCL, and GIST
- Patient interview on quality of life in advanced RCC patients

Temporal sequence

The following time points were defined as the minimum period for the implementation of the registry:

- Patient Recruitment Phase: January 2008 December 2020
- Recruitment rate: 100 patients/year per product
- Average observation period per patient: 6 months for temsirolimus, 12 months for sunitinib, 6 months for axitinib
- Field Phase: December 2021
- Total duration: 14 years + 1 year evaluation and report (2022)

Since the goal is to keep patients in the registry for life, the registry can be continued indefinitely.

The end of data collection is scheduled for December 2021.

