5 ANALYSIS SETS/POPULATIONS

Analyses will be performed within each indication and treatment, e.g. one for mRCC and temsirolimus, sunitinib and axitinib, one for the non-Pfizer interim therapies and one for MCL and one for GIST.

For data from mRCC patients included prior to amendment VI of the protocol baseline data from sequence 1 will be forwarded as baseline data for sequence 2, if the respective data is not asked for in follow-up 1 of sequence 2 (tumor anamnesis at time of primary diagnosis, prior local and systemic therapies, prior and concomitant diseases, concomitant medication (other than systemic therapy)). Ongoing adverse events from sequence 1 have to be added to the list of concomitant diseases in sequence 2. Additional cancer therapy from baseline and follow-up visits of sequence 1 will be forwarded as baseline data for sequence 2 unless the therapy has been discontinued.

For patients included under amendment VI, baseline data for the second Pfizer treatment will be asked for in the CRF as changes in this data are not completely asked for in the non-Pfizer treatment periods.

For data from mRCC patients the following tables (see chapter 9): demographic information (1.2-1; 1.2-2), study periods (1.1-5.2), previous local and systemic therapy (1.5-1; 1.5-2), duration of therapy (1.6-1), overall survival (2.2-1), progression free survival (2.3-1), course of Karnofsky performance scale (2.5) and course of FKSI-15 (2.6), EQ-5D (2.7) will be repeated for the following groups of patients:

- Treatment sequence 1^{st} sunitinib $\rightarrow 2^{nd}$ axitinib \rightarrow any further therapy
- Treatment sequence 1^{st} temsirolimus $\rightarrow 2^{nd}$ sunitinib \rightarrow any further therapy
- Treatment sequence 1^{st} sunitinib \rightarrow any further therapy (no axitinib in 2^{nd} line)
- Treatment sequence 1^{st} temsirolimus \rightarrow any further therapy
- Treatment sequence 1^{st} sunitinib \rightarrow no further therapy
- Treatment sequence 1^{st} temsirolimus \rightarrow no further therapy
- Any therapy $\rightarrow 2^{\text{nd}}$ axitinib \rightarrow any further therapy.

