8.1.2 Analysis Of Survival Data

OS, PFS and treatment duration will be analyzed using Kaplan-Meier plots. Median, 25% and 75% survival times with confidence intervals for OS and PFS will be presented. For stratification according to physician's prognosis and for risk groups according to Motzer score/MIPI/Fletcher risk table, log-rank tests will be performed.

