11 APPENDICES

11.1 APPENDIX 1: DATA DERIVATION DETAILS

A1.1 Definition and use of visit windows in reporting

Time points for follow-up visits are not determined by the study protocol. It is only suggested to perform those every 8 to 12 weeks. In order to be able to perform statistical analyses, documented visits will be transferred into corresponding time windows.

The definition of single time windows can be taken from the following table:

	Treatment Phase 1	Treatment Phase 2	Treatment Phase 3	Treatment Phase 4	Treatment Phase 5	Treatment Phase 6
Weeks after Baseline	0 to 15	16 to 25	26 to 35	36 to 45	46 to 55	56 to 65
	Treatment Phase 7	Treatment Phase 8	Treatment Phase 9	Treatment Phase 10	Treatment Phase 11	and so on
Weeks after Baseline	66 to 75	76 to 85	86 to 95	96 to 105	106 to 115	
	Survival 1	Survival 2	Survival 3	Survival 4	Survival 5	and so on
Months after discontinuation	0 to 15	16 to 21	22 to 27	28 to 33	34 to 39	

In case more than one visit was performed within one time window, than the later one

In case more than one visit was performed within one time window, than the later one will be used for analyses "by time windows" with the following exceptions:

- Adverse events will be analyzed from all documented visits.
- Duration of PFS will be determined using the first occurrence of a progression of disease.

The study phase while patients are treated with Torisel[®]/Sutent[®] is defined as follow-up phase. The follow-up of subjects after discontinuation of Torisel[®]/Sutent[®] is defined as survival phase.

A1.2 Definition of Analysis Populations/Sets

Not applicable.

A1.3 Further Definition of Endpoints

Demography

```
Age (years) = (date of baseline visit – date of birth + 1)/365.25

BMI = body weight (kg) / body height (m)**2
```

Oncological history

For computation of duration of RCC, MCL and GIST and time since first confirmed metastasis (not for MCL) an arbitrary day 1 will be added and thereafter the SAS function for computing with date values will be used.

```
Duration of RCC/MCL/GIST (months) = (1/month/year \text{ of start of } Torisel@/Sutent@/Inlyta@ treatment } - 1/month/year of date of histological confirmation of RCC/MCL/GIST)*12/365.25
```

First metastases (months) = (1/month/year of baseline visit - 1/month/year of date of first confirmation of metastasis)*12/365.25

Survival

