In case an event (either death or progression) was present and date of event was documented, the following definitions was used:

Overall Survival (OS, months) = $\frac{\text{date of death} - \text{date of baseline visit} +1}{365.25 *12}$

Progression Free Survival (PFS, months) = (minimum of (date of death, date of progression) – date of baseline visit + 1)/365.25 * 12.

In case information on dates were partly or completely missing or contradictory, the following was done:

• PFS:

- o the presence of a progression was confirmed, but no date was documented: if date of last intake of study medication was given, this date was used as date of progression, otherwise the date of the last visit with a documented "non-progression (e.g. SD)" was used as date of progression.
- o the presence of a progression was confirmed, but dates within a visit and on final documentation were contradictory, the prior date was used.
- o in case a death was documented within a survival follow-up/ within sequence 2 for subjects from sequence 1, but no progression was documented within regular study, the date of last visit + 1 day was used as date of progression.
- o in case no progression was documented, subject was censored with the latest available contact date / assessment date within study/within sequence.
- o in case these rules led to a missing duration or a negative duration, duration was set to "1 day".

• OS:

- o in case a death was documented, but date of death was unknown, the date of death was substituted with the latest available date for the patient (last visit, last contact date, date of assessment)
- o in case no death was documented, subject was censored with the latest available contact date / assessment date within study.
- o in case these rules led to a missing duration or a negative duration, duration was set to maximum of (PFS,"1 day").

Response to therapy (Recist criteria/ Cheson criteria)

Response to therapy according to the Recist/ Cheson criteria will be analyzed using the physician's assessment as documented in the CRF. As neither "size of lesion", "new lesions" or "increase in size" are defined as key fields, contradictory answers will not overvote physicians assessment.

"Best response" will be analyzed using the physician's assessment at final visit. If "Best response" is missing it will be determined from the best response documented during previous follow-up visits.

Treatment

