Treatment duration (weeks) = (date of death or date of drop-out or date of end of treatment with Torisel®/ Sutent® - date of first infusion within the registry + 1)/365.25 * 52.

Therapy line

for patients with mRCC:

- Splitted therapy (due to coding) was only counted as one therapy line.
- All medication with an identical start date was counted as one therapy line.
- Interferons, interleukins and immunochemotherapies were summarized as "cytokines".
- Ongoing treatment with the medication documented was not counted as line.
- Bisphosphonates and other supplementary treatment will not be considered. for patients with MCL:
 - Splitted therapy (due to coding) was only counted as one therapy line.
 - All medication with an identical start date was counted as one therapy line.
 - Rituximab maintenance therapy and stem cell transplantation, both connected with previous immunochemotherapy (ATC L01 Antineoplastic agents and L03 Immunostimulants), were not counted as line.

Rituximub were counted as maintenance therapy, if

- physician's comment contained free text / phrases like "Erhaltung", "Erhalt", "Maintenance" or
- (last therapy prior to Rituximab resulted in remission (CR, PR or MR) and
- Rituximab was started directly after the last therapy (at most one therapy free month was tolerable).)

FKSI-15

For calculation of the FKSI-15 score documented values for questions 1-6, 8,9, 11, 12 and 14 will be reversed by subtracting the documented value from 4. All original scores (for questions 7, 10, 13 and 15) and all reversed scores will be summed, multiplied by 15 and devided by the number of answered questions resulting in a score within a range from 0 to 60. The FKSI-15 score cannot be determined if more than 7 questions are not answered.

FKSI-DRS score will be calculated like the FKSI-15 score considering only questions 1, 3, 4, 5, 6, 8, 11, 12 and 14 (multiply by 9). FKSI-DRS cannot be determined if more than 4 questions are not answered.

The 4 domains of FKSI-15 will be calculated like the FKSI-15 score. The following tables shows domains and related questions, multiplyer and maximal number of unanswered questions in order to give a valid score.

Domain	Questions	Multiplyer	Maximal number of unanswered questions
Signs and symptoms	1, 2, 3, 4, 5, 6, 12, 13	8	4
Respiratory symptoms	8, 11	2	1
Quality of life	7, 10, 13, 15	4	2
Emotional symptom	9	1	0

EQ-5D (TTO)

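### The SAP converts treatment duration to weeks with /365.25 × 52, which implies a 7.024-day week and understates each duration by a constant 0.34%

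*SAP*

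**What the plan says.** SAP Appendix 1, A1.3 gives the derivation under Treatment. It opens with "Treatment duration (weeks) = (date of death or date of drop-out or date of end of treatment with" the named products, subtracts the start date, and ends with "date of first infusion within the registry + 1)/365.25 * 52". The unit is stated as weeks. Neither document defines a week as anything other than seven days or explains the factor 52.

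The other derivations in the appendix use the same year length. Age in years ends with "date of birth + 1)/365.25". Disease duration, overall survival (OS) and progression-free survival (PFS) are expressed in months with the factors 365.25 and 12.

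Treatment duration is an analysed variable. SAP 8.1.2 states that "OS, PFS and treatment duration will be analyzed using Kaplan-Meier plots". SAP section 5 includes "duration of therapy (1.6-1") among the tables to be repeated for the mRCC treatment sequences.

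**The concern.** Multiplying by 12 after dividing by 365.25 is coherent, because a year has exactly twelve months. Multiplying by 52 is not, because 365.25 days contain 52.18 weeks of seven days. The formula therefore returns a number labelled weeks that is not in weeks, and the error has the same sign for every patient.

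A derivation appendix is written to be programmed literally. If this line is, any treatment duration reported in weeks will be slightly too short: each patient value, and each mean, median or quartile derived from those values. What is at stake is the accuracy of a descriptive result and its unit label, not any inference.

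**Working it through.** **Inputs**

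- Conversion: inclusive day count d (end − start + 1), divided by 365.25 and multiplied by 52 (SAP A1.3, Treatment).
- Length of a week: 7 days. This is the ordinary meaning; the documents give no other.
- Durations used to size the effect: the Protocol, section 6, gives average observation periods of "6 months for temsirolimus, 12 months for sunitinib, 6 months for axitinib". I use 183 and 365 days for these, with 84 and 730 days as a shorter and a longer case.

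The documents give no numerical treatment duration, so there is no stated figure to reproduce.

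**Step 1: implied week.** 365.25 / 52 = 7.0240 days. A year of 365.25 days holds 365.25 / 7 = 52.179 weeks, not 52.

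**Step 2: ratio to seven-day weeks.** (d / 365.25 × 52) / (d / 7) = 52 × 7 / 365.25 = 364 / 365.25 = 0.99658. The day count d cancels, so the factor is the same for every patient. The shortfall is 1 − 0.99658 = 0.342%. Going the other way, the correct value exceeds the SAP value by 365.25 / 364 − 1 = 0.343%.

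**Step 3: size in weeks and days.**

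| Days d | SAP: d/365.25 × 52 | d/7 | Shortfall (weeks) | Shortfall (days) |
|---|---|---|---|---|
| 84 | 11.959 | 12.000 | 0.041 | 0.29 |
| 183 | 26.053 | 26.143 | 0.089 | 0.63 |
| 365 | 51.964 | 52.143 | 0.178 | 1.25 |
| 730 | 103.929 | 104.286 | 0.357 | 2.50 |

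**Step 4: visibility after rounding.** The SAP states no number of decimals for this variable. If one decimal is assumed, the two formulas first differ at 20 days (2.8 against 2.9). They still agree at some later values, the last being 183 days (both 26.1), and they differ at every whole day from 184 onwards.

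**Step 5: what the factor leaves alone.** Multiplying all durations by one constant preserves their order, so Kaplan-Meier step heights are unchanged and only the time axis is rescaled. Ratios of durations between drugs or sequences are unchanged, and absolute differences in weeks shrink by the same 0.34%. OS, PFS and disease duration use 365.25 with 12 and do not contain this error.

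**The case against.** The strongest reply is that nothing turns on it. The Protocol (section 11, Biometric evaluation) calls the evaluation purely descriptive, and SAP 4.1 and 4.2 list hypotheses and decision rules as not applicable. The shortfall is about half a day at 6 months and just over a day at 12 months. All of that stands, and it limits the point to a minor correction. It does not make the formula right.

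Several stronger readings are tempting, but the documents do not support them.

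- **A mismatch with the visit windows.** A1.1 labels its windows "Weeks after Baseline", so a reader might infer that durations and windows will disagree. The windows assign visits and count from baseline, whereas treatment duration counts from the first infusion. Nothing in the plan maps one to the other.
- **A distorted Kaplan-Meier result in Table 1.6-1.** The description of that table is not readable in the public SAP, so its unit, decimals and contents are unknown. SAP 8.1.2 promises plots for treatment duration, but it names median and quartile times with confidence intervals only for OS and PFS.
- **A fixed duration beyond which the error shows.** The shortfall reaches 0.05 weeks at about 15 weeks, but that is not a visibility threshold. As Step 4 shows, rounding decides case by case until 184 days.

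It can also be said that the same line has larger problems. It starts at a first infusion although sunitinib and axitinib are described as oral, its end date names only two of the three products, and Protocol section 11 starts the duration at inclusion in the registry. Those passages need to be reconciled, and a difference of a day or two in the start date would outweigh the conversion error for most patients. They are separate matters, and settling them would not correct the factor.

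**Conclusion.** Wrong as written, minor. As defined, treatment duration in weeks is too low by a constant 0.34%: about 0.09 weeks at 6 months and 0.18 weeks at 12 months. The conclusion rests on a seven-day week and on the line being programmed literally; the shortfall is measured against the SAP's own inclusive day count. No conclusion about survival, progression, patient ordering or relative comparison of groups depends on it.

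**What to change.** In SAP A1.3, replace /365.25 * 52 with /7, so that treatment duration (weeks) = (end date − start date + 1)/7, keeping whatever start and end dates are settled on for that definition. The cost is one line of SAP text and one line of code, with no change to data, analysis sets or endpoints.

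There is one small consequence to manage. SAP section 3 plans two interim analyses per year and a final analysis of identical content, and Protocol 12.1 plans to present interim results as abstracts. Whether treatment durations already presented used the present factor is not stated. If they did, the final report should note that durations in weeks rise by 0.34% because the conversion was corrected.

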The Summary of Product Characteristics of sunitinib is part of this observational plan.

Information on Inlyta® (axitinib)

The oral multikinase inhibitor Inlyta® (active substance axitinib) is a "small molecule". Axitinib is a potent and highly selective tyrosine kinase inhibitor of the vascular endothelial growth factor receptors VEGFR-1, VEGFR-2, and VEGFR-3, involved in pathological angiogenesis, tumor growth, and metastases. Axitinib has been shown to be a potent inhibitor of VEGF-mediated endothelial cell proliferation and cell survival. Inlyta® is used according to the Summary of Product Characteristics. The named contraindications, warnings and precautions for use, side effects, interactions and instructions on the dose, type and duration of the application should be observed.

[figure not shown]

The Summary of Product Characteristics of axitinib is part of this observational plan.

Patient Interview Advanced RCC

For the patient interview, the validated FKSI-15 questionnaire and the validated EQ-5D questionnaire/VAS will be used to document the effect of the substances temsirolimus and/or sunitinib and/or axitinib by the patient.

The Functional Assessment of Cancer Therapy-Kidney Symptom Index-15 (FKSI-15) includes 15 questions subdivided into 4 groups. Signs and symptoms, respiratory symptoms, quality of life, emotional symptoms. EuroQol-5D (EQ-5D) includes EQ-5D Index and EQ-Visual Analog Scale (VAS). The EQ-5D in turn is divided into 5 groups: Mobility, independence, usual activities, pain/discomfort, and anxiety/depression.

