The biometric evaluation of the patient data (including statistical analysis plan) takes place, appropriate to the design of a registry, in a purely descriptive manner, and will be performed by a Contract Research Organization (Winicker Norimed GmbH, Nuremberg). An annual interim analysis will be performed.

Definition of analysis set

All prospectively documented patients with a histologically confirmed diagnosis of renal cell carcinoma, MCL, and GIST will be included in the "safety population".

All patients to whom at least one of the following criteria apply will be included in the "efficacy population": Date of death, time of progression, physician's assessment of therapy response, or therapy assessment of efficacy and tolerability by the physician are available.

Retrospectively documented information will not be included in the analysis.

Analysis of Safety Criteria

The absolute and relative frequency of patients with adverse events will be shown in a tabular form, both globally and according to the system organ classes and the MedDRA "preferred terms". In addition, the absolute and relative frequency of therapy dropouts will be presented both overall and according to discontinuation reasons. Serious adverse events will be evaluated separately. Previous and concomitant therapies will also be tabulated.

Laboratory analysis and electrocardiogram results will be analyzed per visit. In addition, the physician will assess information on tolerability during therapy.

Analysis of Efficacy Criteria

The change in disease activity will be described using the following parameters:

[figure not shown]
- Assessment of response to therapy by the physician
- Physician's assessment of efficacy
- Overall survival (OS)
- Progression-free survival (PFS)
- Maximum Response

For the analysis in STAR-TOR, the duration of treatment is defined as the period between inclusion in the registry and occurrence of any of the events of either death or discontinuation of the documentation or termination of therapy.

The duration of treatment will be evaluated using methods from the field of "survival time analysis".

Other analysis parameters

Comorbidities will be coded in accordance with MedDRA and concomitant medications according to WHO-DD. Frequencies for appropriate coding levels will be presented. Evaluation of sequence and therapy regimens and quality of life (advanced RCC) will be performed.

Case number estimate

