3 INTERIM ANALYSES

Two interim analyses are planned per year. A final analysis after end of study is planned with identical content. The analyses to be performed and the tables to be presented are defined in this statistical analysis plan (SAP).

Interim analyses are performed in order to get and to present early information on safety and effectiveness of a treatment with temsirolimus, sunitinib or axitinib in the usual health care setting. Interim analyses are also performed in order to get answers on new scientific questions.

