2.5-1	Course of ECOG performance status	MCL	EAS	Frequency table by time windows and for the last documented visit, shift table for differences to baseline (in total and by patient risk groups)
2.5-2	Course of B-symptoms	MCL	EAS	Frequency table by time windows and for the last documented visit
2.6	FKSI-15: Course			
2.6-1	Course of FKSI-15 score	mRCC	EAS Sequence analysis	Sample statistics by time windows and for the last documented visit and absolute and relative change to baseline.
2.6-2	Course of FKSI-DRS score	mRCC	EAS Sequence analysis	Sample statistics by time windows and for the last documented visit and absolute and relative change to baseline.
2.6-3	Course of FKSI domains	mRCC	EAS Sequence analysis	Sample statistics by time windows and for the last documented visit and absolute and relative change to baseline.
2.7	EQ-5D: Course			
2.7-1	Course of EQ-5D: domains	mRCC	EAS Sequence analysis	Frequency tables by time window and for the last documented visit and shift tables to baseline
2.7-2	Course of EQ-5D-VAS	mRCC	EAS Sequence analysis	Sample statistics by time windows and for the last documented visit and absolute and relative change to baseline.

Table No.	Title	Treatment/ Indication	Analysis set	Description
2.7-3	Course of EQ-5D: TTO	mRCC	EAS Sequence analysis	Sample statistics by time windows and for the last documented visit and absolute and relative change to baseline.
3	Safety			
3.1	Display of adverse events (AE)			
3.1-1.1	Summary of adverse events	All	Safety	No. / % of patients - at risk - with AE - with drug related AE - with AE related to Pfizer treatment - with AE related to interim treatment - with SAE - with drug related SAE - with SAE related to Pfizer treatment - with SAE related to Pfizer treatment - with SAE related to interim treatment - with AE leading to permanent discontinuation of Torisel®/ Sutent® / Inlyta® - with drug related AE leading to permanent discontinuation of Torisel®/ Sutent® / Inlyta® - with SAE leading to permanent discontinuation of Torisel®/ Sutent® / Inlyta® - with drug related SAE leading to permanent discontinuation of Torisel®/ Sutent® / Inlyta® - with drug related SAE leading to permanent discontinuation of Torisel®/ Sutent® / Inlyta® - Death No. / % of AE - all AE - drug related - related to Pfizer treatment - related to interim treatment - SAE - drug related SAE - SAE related to Pfizer treatment - SAE related to interim treatment

Table No.	Title	Treatment/ Indication	Analysis set	Description

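### The SAP's FKSI-15 domain table counts item 13 in two domains and item 14 in none, so the Signs and symptoms score is misdefined

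*SAP*

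**What the plan says.** Protocol 5.2 (Patient Interview Advanced RCC) describes the FKSI-15 as an instrument that "includes 15 questions subdivided into 4 groups": signs and symptoms, respiratory symptoms, quality of life and emotional symptoms.

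SAP Appendix 1, A1.3 gives the scoring. Items 1-6, 8, 9, 11, 12 and 14 are reversed by taking 4 minus the answer, and then "All original scores (for questions 7, 10, 13 and 15) and all reversed scores will be summed". The sum is multiplied by 15 and divided by the number of items answered, for a range of 0 to 60. The FKSI-DRS is scored in the same way, "considering only questions 1, 3, 4, 5, 6, 8, 11, 12 and 14", with multiplier 9. For the domains, "The 4 domains of FKSI-15 will be calculated like the FKSI-15 score". A table gives each domain's items, its multiplier and the "maximal number of unanswered questions in order to give a valid score":

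| Domain | Multiplier | Max. unanswered | Items as printed |
|---|---|---|---|
| Signs and symptoms | 8 | 4 | 1, 2, 3, 4, 5, 6, 12, 13 |
| Respiratory symptoms | 2 | 1 | 8, 11 |
| Quality of life | 4 | 2 | 7, 10, 13, 15 |
| Emotional symptom | 1 | 0 | 9 |

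The domains are reported in SAP section 9, Table 2.6-3 ("Course of FKSI domains"), for mRCC in the effectiveness set, as sample statistics with absolute and relative change from baseline. SAP section 5 repeats the FKSI-15 tables for seven mRCC treatment-sequence groups.

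**The concern.** Four groups that divide 15 questions should use each question once. The printed rows use item 13 twice and item 14 not at all.

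A1.3 is the derivation specification, so a programmer who follows it literally would build a Signs and symptoms score from seven symptom items plus one item already counted under Quality of life. A change in item 14 would move the FKSI-15 total and the FKSI-DRS but would show in no domain.

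The error would also recur. SAP section 3 says "Two interim analyses are planned per year" and gives the final analysis the same content, so a mistake in the code would be carried through every run.

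**Working it through.** **The parts that are right.** The reversed items (11 of them) and the unreversed items (7, 10, 13, 15) together cover 1 to 15 once each. The maximum total is 15 × 4 = 60, which reproduces the stated 0-60 range. Each multiplier equals the number of entries in its row, and each limit on unanswered items is half that number, rounded down (8→4, 2→1, 4→2, 1→0).

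**Item count.** The rows hold 8 + 2 + 4 + 1 = 15 entries but only 14 distinct items. The duplicate is 13 and the absent item is 14.

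**Which entry is the slip.**
- Item 14 is the only item without a domain.
- The four unreversed items are exactly the Quality of life row, so 13 fits there. In the Signs and symptoms row, 13 is the only unreversed item.
- Item 14 is reversed, as are the other seven Signs and symptoms items.
- Eight of the nine FKSI-DRS items lie in Signs and symptoms or Respiratory symptoms. Item 14 is the ninth and lies in no domain.

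With 14 in place of 13 in the first row, the table has 15 entries and 15 distinct items. The multiplier of 8 and the limit of 4 stay correct, and all nine FKSI-DRS items fall in the two symptom domains.

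**Effect, complete questionnaires.** Let x13 and x14 be the raw answers, each 0 to 4. Item 13 is scored x13 and item 14 is scored 4 - x14. Printed minus evidently intended score is

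d = x13 - (4 - x14),

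which runs from 0 - 4 = -4 to 4 - 0 = +4 on a scale of 0 to 8 × 4 = 32. Over the 25 possible answer pairs:

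| d | -4 | -3 | -2 | -1 | 0 | +1 | +2 | +3 | +4 |
|---|---|---|---|---|---|---|---|---|---|
| Pairs | 1 | 2 | 3 | 4 | 5 | 4 | 3 | 2 | 1 |

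The difference is zero in 5 pairs and at least 2 points in size in 2 × (1 + 2 + 3) = 12 pairs. These count possible answers. They are not patient frequencies.

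**Effect on change from baseline, complete questionnaires at both visits.** Since d = x13 + x14 - 4, the constant cancels, and the error in a patient's change is (change in x13) + (change in x14). The error in a mean change is the sum of the two mean changes. The documents give no response data to put into this.

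**Effect, incomplete questionnaires.** With both items answered and k of the seven shared items answered,

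d = 8/(k + 1) × [x13 - (4 - x14)].

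| Items answered (k + 1) | 8 | 7 | 6 | 5 | 4 |
|---|---|---|---|---|---|
| Largest absolute d | 4 | 32/7 = 4.57 | 32/6 = 5.33 | 32/5 = 6.4 | 32/4 = 8 |

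If only one of items 13 and 14 is answered and k = 3, one list has 4 answered items (valid) and the other has 3, that is 5 unanswered (not determinable). If neither is answered, the two lists give the same score.

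**The case against.** **The impact is small.** The evaluation is "in a purely descriptive manner", the SAP has no hypotheses or decision rules, and the domains appear only in one supporting table for one indication. This stands. It limits the weight of the point but does not make the row correct.

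**The intended entry is inferred.** The item wording is not printed and the SAP's reference list has no FKSI source. The multipliers summing to 15 is weak evidence, because the faulty rows also sum to 15. This stands in part. The duplicate and the omission can be read directly from the table. The replacement by 14 rests on the reversal list, the FKSI-DRS list and the protocol's description of four groups, all of which agree. Deliberate overlap would not explain why item 14 drops out of every domain.

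**The figures are single-questionnaire extremes.** The 8-point case needs half the domain unanswered. This stands: no shift in a mean can be estimated from the documents, and items 13 and 14 may move so that the errors partly cancel.

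**The program may already be right, or one digit of the table may have been misread from the PDF.** Neither can be excluded. The row otherwise reads cleanly, and a look at the SAP page and the code settles both.

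**Conclusion.** The concern holds. As written, the Signs and symptoms domain contains an item that also belongs to Quality of life, and item 14 has no domain. On the evident reading (14 for 13), the score is off by -4 to +4 of 32 points for a complete questionnaire and by up to 8 points with the fewest answers allowed. In one missing-data pattern the score also changes between valid and not determinable.

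This assumes that the four domains were meant to use each item once and that the program follows the printed row. The reach is one domain in Table 2.6-3, overall and by treatment sequence. No conclusion on survival, response, safety, the FKSI-15 total or the FKSI-DRS depends on it. It should be fixed because it is a wrong scoring rule for a reported patient outcome and costs little to correct.

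**What to change.** 1. Check the domain table against the FKSI-15 scoring source, and add that source to SAP section 10.
2. If confirmed, change the Signs and symptoms row to items 1, 2, 3, 4, 5, 6, 12, 14, with the multiplier of 8 and the limit of 4 unanswered unchanged.
3. Check which item list the analysis program uses. As a test on complete questionnaires, the four domain scores must add up to the FKSI-15 total. With the printed row they miss it by x13 - (4 - x14).
4. Only if the program follows the printed row, rerun the Signs and symptoms part of Table 2.6-3, overall and by treatment sequence, and review earlier interim outputs of that domain, including any abstract that reported it.

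The cost is a one-number SAP correction and one program check. If the code shares the error, add the rerun of one domain in one table and the review of past outputs. No new data are needed.
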